# 3.2.1.2 Exclusion Criteria

This study will include subjects who do not meet the following criteria:

- 1. Participation in a clinical trial within 30 days prior to entry into this study and/or during the period of study participation,
- 2. Previous intraocular or corneal surgery in either eye, including refractive surgery (e.g., LASIK),
- 3. Progressive sight threatening disease or other previous or current ocular conditions, other than myopia, that may predispose for future complication (e.g., diabetic retinopathy, pseudoexfoliation, retinal detachment, ocular hypertension or glaucoma, clinically significant corneal disease (Fuchs, keratoconus, herpes simplex or zoster keratitis), retinal vascular disease, cataract, etc.) in either eye,
- Low/abnormal corneal endothelial cell density (ECD) according to recommendations in ISO-11979-10 (Tab. A.1),
- 5.
- 6. Amblyopia,
- 7. Presence of active or history of chronic inflammation in either eye (e.g., scleritis, uveitis, etc.),
- 8. Clinically significant irregular astigmatism in either eye, as determined by the Investigator,
- 9. Serious (i.e., life threatening), acute, chronic or systemic, non-ophthalmic disease or illness that would increase the operative risk, confound the outcome(s) of the study or which may preclude study completion (e.g., immunocompromised, connective tissue disease, clinically significant atopic disease, uncontrolled diabetes, insulin dependent diabetes, etc.),
- 10. Use of topical steroids at time of implantation,
- 11. Systemic or topical medication, other than prescribed study medications (e.g., systemic corticosteroids, anti-metabolites) that may confound the outcome or increase the risk to the subject,
- 12. Allergy to anesthetics or other postoperative medications required in this study,

- 13. Subject who is pregnant, plans to become pregnant, or is lactating during the course of the study, or has another condition associated with the fluctuation of hormones that could lead to refractive changes,
- 14. Subjects who, in the judgment of the Investigator, present any emotional, physiologic, or anatomical condition which may preclude participation in this study or provide an inappropriate landscape for the intended study treatment.

#### 3.2.2 Subject Completion

The subject has completed the entire study when the study lenses have been implanted bilaterally and the Sponsor receives completed CRF documentation for all visits. Subjects who require further follow-up for an adverse event (AE) will be followed according to Section 6.3.5.

A Study Exit CRF for each eye must be completed for all subjects who complete the study.

#### 3.2.3 Subject Discontinuation

A subject may be discontinued (at the discretion of the Investigator, the Sponsor and/or the EC) prior to the final study visit for several reasons, including, but not limited to:

- voluntary withdrawal
- death
- surgical complication preventing implantation of the study lens
- explant of the study lens(es)

If the study lens is explanted, a minimum of one post-explant visit should be completed to record safety measures for the subject (e.g., BCDVA, cataract/lens evaluation, endothelial cell count, etc.).

Prior to discontinuing a subject, every effort should be made to contact the subject, schedule a final study visit, and obtain as much follow-up data as possible.

Adverse events will be followed as described in Section 6.3.5. Subject withdrawals will be documented clearly on the source document and applicable CRF.

Only subjects who do not receive successful bilateral implantation MAY be replaced. Subjects who are discontinued from the study following treatment will not be replaced.

Discontinued subjects should be followed outside of the study protocol according to the Investigator's normal postoperative standard of care.

#### 3.2.4 Lost to Follow-up

Subjects who do not return for postoperative Visit 5, as defined by the visit window and cannot be contacted, will be considered lost to follow-up. All follow-up attempts will be documented in the subject's source documentation, and the applicable CRFs will be completed.

### 3.3 Investigators

- The study will be conducted at approximately 6 clinical site(s) located in Europe (Spain, Belgium and Germany).
- The study will be conducted by Investigators who have completed the STAAR Surgical EVO Visian ICL Physician Certification Program and are determined by STAAR Surgical to be suitably qualified by training and experience to conduct this study in compliance with all applicable GCPs and local regulations. Sub-Investigators will be identified on the Device Investigator Agreement (DIA)/ Delegation of Authority Log (DOA).
- Each Investigator will enroll approximately 10 subjects (20 eyes). In the event that selected sites do not meet full enrollment, the Sponsor may decide to increase enrollment as needed at other currently active sites and additional site(s) may be added to satisfy the enrollment requirements of the study.

# 3.4 Study Duration

The duration of the study, including the time to recruit all subjects, will be approximately 18 months. Eligible subjects who are enrolled in the study will be seen for 7 scheduled study visits (per eye) over the course of approximately 6-9 months.

# 4.0 STUDY MATERIALS

#### 4.1 Description of Investigational Device

The EVO+ Visian ICL with Aspheric (EDOF) Optic includes a refractive optic and features a single piece lens design with a convex/concave optic zone of 4.9 to 6.1 mm diameter (according to model and power) and a 0.36 mm diameter central hole in the optic known as the KS-AquaPORT®. The lens is manufactured in five overall diameters: 11.6, 12.1, 12.6, 13.2, and 13.7 mm to accommodate different eye sizes. The lens is manufactured from Collamer, a proprietary polymer made from collagen, hydroxyethylmethacrylate (HEMA) and an ultraviolet (UV) absorber. The 10% UV cut-off for the ICL is at 387 nm wavelength. The lens is supplied with a delivery system for implantation through an incision of 3.5 mm or less. STAAR will provide the following materials:

- EVO+ Visian ICL with Aspheric (EDOF) Optic
- Supplemental lens for each eye
- MICROSTAAR injector MSI-PF or MSI-TF reusable injector with SFC-45, single use cartridge and foam tip plunger (FTP)

The study lenses will be packaged and labeled in a manner consistent with the study design and applicable regulations.

#### 4.2 Instructions for Use and Administration

#### 4.2.1 Surgical Procedure

Surgery to implant the EDOF ICL will be performed in accordance with instructions provided in Appendix B.

#### 4.2.2 Storage Requirements

The study lenses are to be stored at room/ambient temperature. The storage location at the clinical site must have limited access, available to study site personnel only.

# 4.3 Treatment Replacement

A supplemental lens will be provided for each eye. Study lens accountability should be maintained as described in Section 4.6.

#### 4.4 Other Materials

STAAR will provide the following ancillary materials for use during the study:

- M&S Clinical Trial Suite Vision Tester
- iTrace Aberrometer

# 4.5 Packaging and Labeling

The Study Lenses will be packaged and labeled in a manner consistent with the study design and applicable regulations. In addition to the standard labelling of the product, a study-specific label will be attached to the outer packaging and will contain information as required by EN ISO 14155 and local labelling requirements together with caution statement that it is for clinical trial use only.

# 4.6 Accountability

The Investigator will be responsible for keeping current and accurate records of all study lenses received, dispensed, and returned to the Sponsor. The study lenses must be stored under the appropriate conditions in a secure, limited access area and are to be implanted only in subjects enrolled in the study, in accordance with the conditions specified in this protocol.

Accountability records will include:

- Serial number of each study lens
- Date received by site
- Names of site personnel who receive, use and dispense the study lens
- Date of dispensation/use
- Subject treated with each study lens
- Date of return to Sponsor and reason (e.g., damaged, defective, back-up not used), if applicable

At time points throughout the study and/or upon completion of the study, the Sponsor/Sponsor's representative will review and verify the Investigator's accountability records. Following verification, and as directed by the Sponsor, all unused or explanted study lenses must be returned to the Sponsor, as directed.

#### 4.6.1 Treatment Allocation

All patients at study sites who provide informed consent to participate and meet all eligibility criteria will be offered the opportunity to enroll in this study in a consecutive manner. Upon enrollment, subjects will be assigned the next available Subject ID number.

#### 4.7 Risk Assessment

The EVO+ EDOF ICL has been assessed for risk control measures per established risk analysis and FMEA reports. The use of CE-Marked model in the context of this clinical study requires the residual risk to be balanced against the anticipated benefit of the procedure. The risk level has been determined to be in the lowest category, deeming the risk to be acceptable, and it is believed that the benefits outweigh any of the identified or associated residual risks with this clinical evaluation.

If new information regarding new risks to patients is made available during the course of the study, the EC and applicable regulatory agencies will be notified, the informed consent will be updated and the Investigator will be required to provide new information to patients and have them sign the revised ICF.

# 5.0 STUDY CONDUCT

# 5.1 Study Visits

All Subjects who meet the eligibility criteria will be seen according to the following schedule.

Preoperative Visit	Days -90 to 0
Operative Visit	Day 0
Postoperative Visit 1	Day 1 (1 day)
Postoperative Visit 2	Week 1 (5 – 9 days)
Postoperative Visit 3	Month 1 (3 – 5 weeks)
Postoperative Visit 4	Month 3 (10 – 14 weeks)
Postoperative Visit 5	Month 6 (21 – 26 weeks)

Refer to Appendix A for a schedule of visits and parameters and Appendix C for methods of clinical evaluation.

Following identification of a potential subject, the Investigator (or designee) will explain the purpose of the study, procedures, risks/benefits, and subject responsibilities to the potential subject. The subject's willingness and ability to meet the follow-up requirements of the study will be determined. If the subject chooses to participate in the investigation, written informed consent will be obtained. The subject and the person obtaining written consent, will sign and date the EC-approved ICF. The original signed document will be retained in the subject records, and a copy will be provided to the subject. In addition, the applicable privacy regulation requirements must be met.

#### 5.1.1 Preoperative Visit – Days -90 to Day 0

Prospective subjects who have provided informed consent will be screened to determine eligibility for treatment in the study. Demographic information, relevant ocular medical history, and current ocular medication use will be collected. The preoperative clinical evaluation will consist of a complete ophthalmic examination conducted no more than 90 days prior to surgery.

Refer to Appendix A: Schedule of Visits and Parameters for assessments to be performed.

#### 5.1.2 Operative Visit – Day 0

Subjects will be reassessed to confirm eligibility. In addition, any changes in concomitant medications or AEs will be recorded. If the subject no longer meets eligibility criteria, he/she will be considered a screen failure. If the subject is eligible, he/she will be enrolled in the study and undergo surgery according to the surgical procedure described in Appendix C. If the study lens is not implanted due to a surgical complication, the subject will be discontinued from the study.

At approximately 1-6 hours after surgery, an intraocular pressure (IOP) reading in the implanted eye(s) will be conducted. Any complications, AEs, or associated treatment given will be appropriately documented and reported.

#### 5.1.3 Postoperative Visits – Day 1 to Month 6

Each treated subject will be seen for 5 postoperative visits according to the schedule in Appendix A.

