# 3.0 STUDY DESIGN

#### 3.1 Description of Study Design

This is a prospective, open-labeled, multi-site evaluation of clinical performance of the CE-Marked EDOF ICL for the improvement of UCNVA. Approximately 48 subjects who meet all eligibility criteria will undergo phakic IOL implantation in both eyes. All eyes will be followed for 6 months after surgery.

The first eye implanted with the study lens and the appropriate time for fellow eye implantation will be determined by the medical judgement of the Investigator. All eyes will be analyzed for safety and performance.

The subject will have completed the entire study when the study lenses have been implanted bilaterally and the Sponsor receives completed case report form (CRF) documentation for all visits. A Study Exit CRF for each eye must be completed for all subjects enrolled in the study.

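### Section 5.1.2 discontinues the whole subject when one eye cannot be implanted, so an already implanted fellow eye can miss Visit 5, leave the primary analysis and be replaced

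*Combined protocol and SAP*

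**What the plan says.** - **Section 5.1.2 (operative visit):** "If the study lens is not implanted due to a surgical complication, the subject will be discontinued from the study". The rule is mandatory and acts on the subject, not the eye.
- **Section 3.2.3 (discontinuation):** a subject may be discontinued, at the discretion of the investigator, the sponsor or the ethics committee. The listed reasons include "surgical complication preventing implantation of the study lens". Before that, "every effort should be made to contact the subject, schedule a final study visit, and obtain as much follow-up data as possible". Afterwards, "Discontinued subjects should be followed outside of the study protocol".
- **Section 3.2.3 (replacement):** "Only subjects who do not receive successful bilateral implantation MAY be replaced". The next sentence reads: "Subjects who are discontinued from the study following treatment will not be replaced".
- **Section 3.1:** "All eyes will be followed for 6 months after surgery". The same section leaves the timing of the second eye to the investigator's judgement and says that all eyes are analysed.
- **Section 5.1.3:** every treated subject has five postoperative visits.
- **Section 7.5 (analysis sets):** the Safety Evaluation Set (SES) holds every implanted eye. The FAS holds only those SES eyes with data for the primary endpoint, and the primary analysis is run on the FAS and the Per Protocol Set, which is drawn from it.

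**The concern.** The eyes may be operated on at different times, and the endpoint is counted per eye, but the exit rule works per subject. Suppose the first eye has the lens and a surgical complication then prevents implantation in the second. Section 5.1.2 discontinues the subject. The first eye still carries the lens and its Visit 5 near acuity could still be measured, but no text keeps it on study until then. Without that measurement it is not in the FAS, and one reading of Section 3.2.3 lets a new subject take its place.

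Two things are at stake. The responder rate is meant to describe implanted eyes, and here implanted eyes can leave the denominator for an administrative reason. Scheduled in-study safety visits for an eye that still holds the device can also be lost.

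**Working it through.** **1. The rules applied to a one-eye subject**

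| Question | Text pointing one way | Text pointing the other way |
|---|---|---|
| Is the subject discontinued? | 5.1.2: yes, mandatory | 3.2.3: discretionary |
| Is the implanted eye seen at Visit 5? | 3.2.3: follow-up moves outside the protocol | 3.1: all eyes for 6 months; 5.1.3: five visits per treated subject |
| May the subject be replaced? | 3.2.3: yes, bilateral implantation was not achieved | 3.2.3: no, if one implanted eye counts as treatment |
| Is the eye in the primary analysis? | FAS: only if endpoint data were collected | 3.1: all eyes are analysed for performance |

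The protocol does not say whether treatment, in the replacement sentence, means one eye or both. Sequential surgery is clearly foreseen. Section 3.4 gives 6 to 9 months of participation per subject, and a footnote to Table A1 covers surgery for either eye being delayed beyond 90 days.

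**2. The plan's own operating characteristics**

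Inputs (Sections 7.2.1 and 7.3): stage 1 has 54 eyes, stopping for futility at 43 or fewer responses and for success at 48 or more. Stage 2 adds 32 eyes, with success at 73 or more of 86. The null rate is 0.75 and the design alternative 0.875. Eyes are treated as independent, as the plan does.

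P(reject) = P(X1 ≥ 48) + Σ over x = 44 to 47 of P(X1 = x) · P(X2 ≥ 73 − x), with X1 ~ Bin(54, p) and X2 ~ Bin(32, p).

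- p = 0.75: 0.0096 + 0.0136 = 0.0232 (stated cap 0.025).
- p = 0.875: 0.4799 + 0.3372 = 0.8171 (stated 0.80).

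The stated figures reproduce.

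**3. Worst case for lost eyes**

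The documents give no frequency for failed second-eye implantation, so the number of lost eyes, k, is an assumption, shown from 0 to 3. Suppose the true rate among all implanted eyes is exactly 0.75, and that for every 86 eyes analysed, k further implanted eyes, all non-responders, were lost and replaced. The rate among analysed eyes is then 0.75 × (86 + k) / 86. Putting this rate into the formula above gives:

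| k | Rate among analysed eyes | Exact type I error |
|---|---|---|
| 0 | 0.7500 | 0.023 |
| 1 | 0.75 × 87/86 = 0.7587 | 0.034 |
| 2 | 0.75 × 88/86 = 0.7674 | 0.050 |
| 3 | 0.75 × 89/86 = 0.7762 | 0.071 |

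If the lost eyes respond at the same rate as the others, the analysed rate stays at 0.75 and the error stays at 0.023 for any k.

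On the estimate itself, a bare pass of 73/86 = 84.9% becomes 73/87 = 83.9% when one lost non-responder is put back.

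**The case against.** The best defence is that the plan already contains the intended answer. Sections 3.1 and 5.1.3 promise follow-up and analysis of all eyes, a final visit is sought before discontinuation, and nothing says that replacing a subject deletes data already collected. The eye remains in the SES, and Section 6.3.5 follows ongoing serious events and device effects until they resolve or no further change is expected. The two replacement sentences can be reconciled if treatment means bilateral implantation; if it means either eye, replacement is barred. All of this is fair, and it limits the damage. It does not close the gap: the final visit need not be Visit 5, the mandatory sentence in 5.1.2 has no exception, and sites must choose between readings.

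Four stronger readings are tempting, and the documents do not support them.

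- **A poor first eye removes its own subject through the eligibility re-check.** Section 5.1.2 does say "If the subject no longer meets eligibility criteria, he/she will be considered a screen failure", and Table A2 repeats eligibility at the second operation. But the following sentence in 5.1.2 has eligible subjects being enrolled, so screen failure reads as a pre-enrolment outcome. Taken literally, exclusion 2 (previous intraocular surgery in either eye) would fail every sequentially treated subject at the second operation, which Section 3.1 shows is not intended.
- **A subject who declines the second eye is dropped.** Nothing makes discontinuation mandatory there. Voluntary withdrawal is a listed reason, but discontinuation in 3.2.3 is discretionary, and being replaceable is not the same as being discontinued.
- **The loss is driven by how the first eye did.** The one route that the text does mandate is a surgical complication in the other eye. The documents do not connect that to the first eye's near acuity.
- **Each swap adds two responders.** At a fixed 86 eyes, dropping one non-responder can raise the count by at most 1. The new subject's second eye fills a place left empty because that eye was never implanted.

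**Conclusion.** The point holds for the surgical-complication route and for the conflicting replacement sentences. As written, the rules allow an implanted eye to be lost to the primary analysis and replaced, against the plan's own commitment to follow all eyes.

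The effect is probably small. The 0.034 figure assumes independent eyes, a true rate exactly at the 0.75 boundary, losses spread evenly over both stages, a lost eye that is certain to be a non-responder, a missed Visit 5, and replacement. Removing any of the last three conditions reduces or removes the inflation. The case for changing the text rests on the contradiction and on how little it costs to resolve, not on a demonstrated bias.

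**What to change.** Reconcile Sections 3.1, 3.2.3, 5.1.2 and 5.1.3 so that study exit is eye-specific for follow-up and counting:

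1. An eye that is not implanted exits. Any implanted fellow eye keeps its scheduled study visits to Visit 5, unless consent is withdrawn, and stays in the SES and the primary analysis.
2. Screen failure applies only before any eye has been implanted.
3. Say whether a one-eye subject may be replaced. If so, replacement does not remove the implanted eye from the analysis.
4. Because the FAS admits only eyes with endpoint data, say how such an eye is counted if its Visit 5 result is still missing. Also say which eyes make up the 54 and the 86: one retained eye plus 43 bilateral subjects gives 1 + 86 = 87, and the decision rule is defined only at 86.

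This changes follow-up and counting only, not clinical management. The cost is a few sentences of protocol text, plus a few one-eye subjects completing visits already scheduled for that eye.

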#### 5.1.4 Unscheduled Visits

Additional visits may be scheduled, as necessary, to ensure the safety and well-being of subjects. All additional exams should be fully documented in the source documents and on Unscheduled Visit CRFs, as appropriate. Visits intended to fulfill scheduled visit requirements that fall outside the designated scheduled visit range, are not Unscheduled Visits. In these cases, the visit data will be collected and transcribed to the appropriate scheduled visit CRF.

If a subject is seen for multiple visits during a given visit timeframe, the data from the visit that is intended to meet the protocol requirements for the scheduled visit should be captured on the visit CRF. Where such a determination cannot be made, the first visit within the scheduled visit interval will be used for completion of the protocol required scheduled visit CRF. Data from any additional visits within a scheduled visit interval will be captured on an Unscheduled Visit CRF.

#### 5.1.5 Missed Visits

If a subject misses any scheduled follow-up visit and cannot be seen prior to the start of the visit range for the next scheduled follow-up visit, the visit will be documented as missed in the source documents and CRFs.

# 5.2 Study Completion

STAAR Surgical will notify the Investigator when to contact the EC to inform them that the study is complete.

#### 5.2.1 Early Study Termination

If during the study it becomes evident to the Sponsor that the study should be stopped prematurely, the study will be terminated and appropriate notification will be given to the Investigator(s), EC, and Local Health Authority, as applicable. STAAR Surgical will instruct the Investigators to stop dispensing study materials/treatment, to assure appropriate follow-up for all enrolled subjects and arrange for study closeout at each site as appropriate.

#### 5.2.2 Post-study Follow-up

If a subject requires further follow-up of a serious adverse event (SAE) upon discontinuation or completion of the study, the Investigator should schedule post-study follow-up visits, as necessary. Refer to Section 6.3.5 for follow-up of SAEs following study exit.

